1. BACKGROUND AND JUSTIFICATION

Developmental dysplasia of the hip (DDH) belongs to the most common disorders of osteoarticular system with public health priorities in generally otherwise healthy infants. Severity can range from a minor acetabular dysplasia to a complete dislocation. Estimates of the incidence of DDH are quite variable and depend on detection methods, ages of the child, and diagnostic criteria etc.¹⁻⁸ A Mongolian study reported that the nationwide hip ultrasound screening by Graf method detected 14.6% of physiologically immature and 1.2% of dysplastic cases.⁹ Another prospective study reported 1.3% incidence of DDH by Graf method of ultrasound.¹⁰ DDH is a multifactorial disorder that genetic and non-genetic factors are involved in its etiology. Contributing factors for the development of DDH are space (big infants), position in utero and hormonal factors (Relaxin) and genetic predisposition.¹¹ In addition, postnatal mechanical factors are also important but not studied thoroughly yet.¹²

Fetal hip joint consists of cartilaginous tissue on a osseous basis. During further maturation, the cartilage is subsequently replaced by bone. Studies have shown that hip joints have a considerable potential for maturation even after birth i.e during the first weeks of life.^{13,14} These unique features allow detect by ultrasound and treat DDH conservatively during this window of opportunity. The early detection and simple treatment with an extension and abduction orthosis in the first weeks of life mostly leads to a maturation and cure of the hip joints, and subsequently, prevents handicaps in children later in life. However, there is still continuing discussion about whether to screen for DDH.^{2,15,16} One point of contention is whether hip joints below the threshold of 60° alpha should be classified as pathological (DDH) or whether a range of physiological immaturity (Graf types 2a / 2a+) is defined where a wait-and-control approach is chosen.^{2,15,17} However, these hips may be vulnerable to persistent dysplasia if postnatal mechanical factors such as swaddling are used in child care. Some studies have found that a history of swaddling to be one of the risk factors for DDH.¹⁸⁻²⁰ Also the swaddling history was more common in late presenting infants with hip dislocation.²¹

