3.2. Sampling and randomization

Study site: The National Center for Maternal and Child Health (NCMCH) is purposely selected as a study site. Approximately 50% of all deliveries in Ulaanbaatar occur in the center and there are about 11,000 live births annually. As the center is a specialized tertiary care level teaching hospital, it is responsible for providing services for follow-up ultrasound controls and treatment of DDH cases in Ulaanbaatar. There are two term-delivery units with 6 neonatologists/screeners, a preterm-

delivery unit with 6 neonatologists/screeners and a pediatric radiology unit with 6 radiologists. Data will be collected from September 2019 to March 2021.

Sample size calculations: The primary outcome of interest is dichotomous (Graf Type 1 or non-Type 1 hips). If we assume that 10% of the subjects on the non-swaddled group has a non-Type 1 hip and it is of clinical relevance only if we observe a 30% (effect size) absolute non-improvement for those on the swaddled group (i.e. 40% of the subjects will have a non-type 1 or worst hip).

For a two-sided test of 5%, a formula to calculate the sample size is given by

$$N (\text{size per group}) = c * \frac{\pi_1(1 - \pi_1) + \pi_2(1 - \pi_2)}{(\pi_1 - \pi_2)^2}$$

where $c = 7.9$ for 80% power, and $\pi_1=0.2$ and $\pi_2=0.4$

For a 80% power, we have $N (\text{size per group}) = 7.9 * [0.1 (1 - 0.1) + 0.4 (1 - 0.4)]/(0.1-0.4)^2 = 29$

Hence minimum $29 * 2 = 58$ subjects are needed.

In order to increase the statistical power, and assuming at least a 20% dropout, it is decided to include about 40 subjects in each group.

Sampling: There are 6 neonatologists/screeners at post-delivery wards of the hospital who perform the hip ultrasound screening. Out of the 6 neonatologists/screeners, one neonatologist will be assigned as a data collector for the study to reduce a baseline diagnostic bias. On the first days after birth, all newborns of the data collector will be screened using Graf's method of ultrasound according to the Mongolian National Guideline.⁸ After the screening, we will generate a list of all newborns with Graf Type 2a hips on daily basis. All term newborns with Graf Type 2a cases (physiologically immature) will be eligible for the study.

Subject inclusion criteria

Predefined inclusion criteria will be:

1. Term newborns with confirmed Type 2a hips
2. Parents who are able to return for the scheduled follow-up ultrasound examination during the study period

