3.5. Statistical analysis

Data will be double computerized using EpiData (The EpiData Association Odense, Denmark) and analyzed using Stata software 9 (Stata Corporation). All ultrasound examination pictures will be uploaded to the HipScreen platform.

Balance checks for the “swaddling” and “non-swaddling” groups will be conducted and reported for all key individual-level variables measured at baseline, including age at hip ultrasound screening in days, gender, risk factors (birth weight ≥ 4000 gr, breech delivery, family DDH history, parity etc.), Graf hip type, alpha angles at baseline and management.

The primary and secondary outcomes will be described as percentage adjusted for the available baseline variables. Outcomes will be evaluated in an intent-to-treat analysis. Univariate analyses will assess factors that will be associated with outcomes and identify potential confounders (with rate ratios of ≥ 2) or variables that differed between study groups at enrollment. These covariates will be included in multivariate analyses. Multivariate logistic regression will be used to estimate the adjusted risks for prevalent outcomes. Pearson's correlation coefficient will be calculated between “non-Type 1” and swaddling days and swaddling hours per day.

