Annex 4. Data analysis plan

Table 1. Baseline characteristics of participants

Characteristics	Non-swaddling	Swaddling	P value*
	N= n(%)	N= n(%)	
Mean age in days at screening (mean ±sd)			
Girls			
Breech position			
Family history of DDH			
Birth weight >4000			
Firstborn baby			
Mean of Graf hip alpha angle at initial screening (mean ±sd)			
Swaddling days			
Swaddling hours per day in			

sd-indicates standard deviation, *DDH* indicates Developmental Dysplasia of the Hip

**chi*² or χ^2 test

Table 2. The associations between the main outcomes and the intervention analyzed by univariate analysis (*chi*² or χ^2 test)

Characteristics	Control	Intervention	OR	P value
	n/N (%)	n/N (%)		
Mean age in days at screening				
Girls				
Breech position				
Family history of DDH				
Birth weight >4000				
Firstborn baby				
Mean of Graf hip alpha angle at initial screening				
None-Type 1 hips				
DDH				
Rim defects at follow-ups				

Table 3. The associations between the main outcomes and the intervention analyzed by multiple logistic model

	Control n/N (%)	Intervention n/N (%)	Adjusted OR*	P
Primary outcome				
None-Type 1				
Secondary outcome				
DDH				
Rim defect				

DDH indicates Developmental dysplasia of the hip, OR indicates odds ratio

**Will be adjusted for significant baseline variables*

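### Annex 4 fixes chi-square tests and an ordinary adjusted odds ratio for DDH and rim defects, which may be too sparse for either at about 32 infants per arm

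*Protocol*

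**What the plan says.** The Protocol's Annex 4 (Data analysis plan) sets out two outcome tables.

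- Table 2 gives univariate comparisons by chi-square, with an OR and P column. Its rows include non-Type 1 hips, DDH and "Rim defects at follow-ups".
- Table 3 is titled "The associations between the main outcomes and the intervention analyzed by multiple logistic model". It reports an adjusted OR and P value for non-Type 1 (primary), DDH and rim defect (both secondary). The footnote adjusts for whichever baseline variables prove significant.

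Section 3.5 names multivariate logistic regression. Covariates are those with a univariate rate ratio of at least 2 or a difference between groups at enrolment: "These covariates will be included in multivariate analyses". Their number is not fixed. Neither section 3.5 nor Annex 4 names an exact or penalised method for sparse outcomes.

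Section 3.2 plans the primary outcome on the assumption that "10% of the subjects on the non-swaddled group has a non-Type 1 hip" and that, in the swaddled group, "40% of the subjects will have a non-type 1 or worst hip". It arrives at a minimum of 29 per group and enrols about 40 per group to allow for at least 20% dropout.

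The only DDH frequencies are in section 1. Nationwide screening "detected 14.6% of physiologically immature and 1.2% of dysplastic cases", and a second study gives 1.3%.

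**The concern.** Ordinary maximum-likelihood logistic regression has no finite log odds ratio for the intervention when one arm has no events. The OR is then zero or infinite, depending on which arm is the reference, and its Wald interval and P value mean nothing. The unadjusted OR in Table 2 fails in the same way. With only a few events and several covariates, an estimate that does exist is unstable. The chi-square approximation is also doubtful when expected counts are below 5.

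DDH is the condition in the trial's title and hypothesis, and these rows carry the comparison of DDH between arms. If the named method fails, a replacement has to be chosen with the results in view. Because Annex 4 names the methods, this is a stated choice that may fit the design badly, and not a detail left open.

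**Working it through.** **Inputs**

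- Test: two-sided 5%, 80% power, c = 7.9 (section 3.2).
- Non-Type 1 rates: 10% non-swaddled, 40% swaddled (section 3.2).
- Enrolment about 40 per group, dropout 20% (section 3.2).
- DDH is a subset of non-Type 1: section 3.4 counts Type 2a+ as physiological, so it is non-Type 1 but not DDH.
- DDH or rim-defect rate in enrolled infants: not given. The rates below are assumptions, shown as a range.

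**The plan's own figure**

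7.9 × [0.1 × 0.9 + 0.4 × 0.6] / 0.3² = 7.9 × 0.33 / 0.09 = 28.97, so 29 per group is reproduced. (Section 3.2 also prints π₁ = 0.2, but both its text and its worked line use 10%.) Allowing for dropout, 29 / 0.8 = 36.25, so 37, which the plan rounds up to about 40. Evaluable per arm: 40 × 0.8 = 32.

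**Chance of no events in one arm**, (1 − p)ⁿ

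| Assumed rate p | n = 32 | n = 40 |
|---|---|---|
| 1% | 72% | 67% |
| 2% | 52% | 45% |
| 3% | 38% | 30% |
| 5% | 19% | 13% |
| 7.5% | 8% | 4% |
| 10% (ceiling, non-swaddled) | 3.4% | 1.5% |

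For example, 0.95³² = 0.194. At n = 32 the chance is at least 50% for rates up to 2.1%, at least 20% up to 4.9%, and below 5% only above 8.9%.

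**DDH as a share of the planned non-Type 1 rates, n = 32**

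With a and b the two arms' probabilities of no events, P(at least one arm empty) = a + b − ab. Expected events = 32 × (p₁ + p₂).

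| Share | Rates (non-swaddled vs swaddled) | Expected events | At least one arm empty |
|---|---|---|---|
| 10% | 1% vs 4% | 1.6 | 80% |
| 25% | 2.5% vs 10% | 4 | 46% |
| 50% | 5% vs 20% | 8 | 19% |
| 75% | 7.5% vs 30% | 12 | 8% |
| 100% | 10% vs 40% | 16 | 3.4% |

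Adjustment makes it slightly worse. In simulation with one continuous and one 50% binary covariate (1,000 trials per scenario), no finite fit existed in 86% of trials at 1% vs 4%, 55% at 2.5% vs 10%, 21% at 5% vs 20% and 3% at 10% vs 40%.

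**Chi-square expected counts**

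With equal arms, each arm's expected event count is half the total, so it is below 5 whenever total events are below 10. Summing the two binomials at n = 32, P(total < 10) is over 99% at 2.5% vs 10%, 73% at 5% vs 20%, 20% at 7.5% vs 30% and 2% at 10% vs 40%.

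**The case against.** **The rate is unknown.** A reader might infer from the 1.2% and 1.3% in section 1 that an empty arm is the likely result, since 0.987³² = 66%. The documents do not support that. Those figures describe all screened newborns, and the 1.2% dysplastic group is reported separately from the 14.6% immature group. The trial enrols Type 2a hips only and excludes confirmed non-Type 2a hips, and its outcome is what those hips show at follow-up. At the 10% ceiling the chance of an empty non-swaddled arm is only 3.4%. For rim defects there is no figure at all. This objection stands: the size can only be given conditionally.

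**Simulated failure rates can mislead.** A reader who simulates the adjusted model with several covariates might conclude that most trials fail even at 5% vs 20%. With four assumed covariates, one of them a 10% binary, some separation did occur in 57% of trials there. Much of that is separation on a covariate, which leaves the intervention OR finite; the intervention OR itself was not finite in 20% to 26% across two runs. The covariate set is also an assumption, because the plan chooses it from the data. This stands too.

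**The DDH evidence would not vanish.** Both tables report n/N (%) by arm, so only the OR and the inference attached to it are at risk. This stands.

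**It may be SAP detail.** A SAP that is not shown could hold a sparse-data fallback, and section 3.5 speaks of logistic regression for prevalent outcomes. The label for the test in Table 2 is also garbled, so a second test may have been meant. This weakens the point but does not remove it. Annex 4 is itself a data analysis plan, lists DDH and rim defect under the logistic model by name, and names only chi-square for Table 2.

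**Conclusion.** The point holds in conditional form. The protocol fixes large-sample methods for two secondary outcomes that may yield few events among about 32 infants per arm, and it names no alternative.

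If the non-swaddled DDH rate is between 1% and 5%, the chance that this arm has no events is 72% down to 19%, and the Table 2 and Table 3 ORs then have no finite log-scale estimate. The risk falls to 3.4% if every planned non-Type 1 hip in that arm is DDH. It is somewhat lower throughout if all 40 per arm are analysed. The chi-square weakness reaches to higher rates: at 5% vs 20% or below, total events are usually under 10.

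These figures rest on assumed DDH rates, independent infants and 20% dropout in each arm. No rate for rim defects can be derived from the document; the same table applies at whatever rate is assumed. The primary outcome at 10% vs 40% is largely unaffected. It would be too strong to say that the planned model will often fail. The case for changing it is that the risk is plausible and the remedy costs almost nothing.

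**What to change.** In section 3.5 and Annex 4, for DDH and rim defects:

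1. Make the main comparison a Fisher exact test or an exact unconditional test (name one), with the risk difference and its Newcombe 95% confidence interval. Both remain usable when an arm has no events.
2. In Table 2, use Fisher in place of chi-square wherever an expected count is below 5.
3. If an adjusted OR is reported for these outcomes, estimate it by Firth penalised logistic regression with a small covariate set fixed in advance, for example arm and baseline alpha angle. Other small prespecified sets would also serve.

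The logistic model for the primary outcome need not change on this account.

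The cost is a few lines of wording, with no new data and no change in sample size. The downside is small: adjusted ORs for these sparse outcomes are limited to few covariates or dropped. The methods remain valid if events turn out to be common.

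### Annex 4 labels post-randomisation swaddling exposure as baseline and adjusts for significant baseline variables, so applying it literally could put the randomised exposure into the intention-to-treat model

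*Protocol*

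**What the plan says.** - **Annex 4, Table 1.** Under the title "Table 1. Baseline characteristics of participants" and beside a P value column, the last two rows are "Swaddling days" and "Swaddling hours per day in" (the row label breaks off there).
- **Annex 4, Table 3.** The adjusted odds ratios for non-Type 1 hips, DDH and rim defect carry the footnote "Will be adjusted for significant baseline variables".
- **Section 3.5.** Covariates for the multivariable model come from two criteria. Univariate analyses are to "identify potential confounders (with rate ratios of ≥ 2"), and the model also takes "variables that differed between study groups at enrollment". The outcome analysis is by intention to treat.
- **Sections 3.1, 3.3 and 3.4.** One arm is assigned 20-24 hours of swaddling a day for 4-6 weeks and the other none. Swaddling hours and days are defined from 24-hour diaries and compliance reports, which are gathered at home visits after randomisation. Section 3.3 assigns the exposure measure to the per-protocol analysis, and Section 3.5 assigns it to a correlation with the primary outcome.

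**The concern.** A baseline covariate must be fixed before allocation. Swaddling hours and days are not: they are the assigned treatment as received. They must differ between arms unless the intervention fails completely, so a significance screen on Table 1 will select them. With hours in the logistic model, the arm coefficient no longer estimates the effect of assignment. It estimates whatever difference remains between infants with the same swaddling hours, and with good adherence almost no such infants exist in both arms. At stake is the adjusted odds ratio for the primary outcome, in a trial designed to detect harm from a common practice.

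**Working it through.** **1. The design figure.** Inputs from Section 3.2: 10% non-Type 1 hips without swaddling, 40% with swaddling, c = 7.9.

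7.9 × (0.1×0.9 + 0.4×0.6) / 0.3² = 7.9 × 0.33 / 0.09 = 28.97, so 29 per group, as stated. The protocol enrols about 40 per group. This figure is not in dispute.

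**2. The arm effect without hours in the model, 40 per group, full adherence.**
- Expected events: 4/40 and 16/40.
- Odds ratio = (16/24)/(4/36) = 6.0; log odds ratio 1.79.
- SE = √(1/4 + 1/36 + 1/16 + 1/24) = √0.382 = 0.62.
- Power of a two-sided 5% two-proportion test: 0.89.

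**3. Would the annex select hours?** In simulated trials, the Table 1 P value for hours was below 0.05 every time, at 0-30% non-adherence. On the Section 3.5 criterion, the design rates for swaddled against non-swaddled give a ratio of 0.40/0.10 = 4, above the threshold of 2.

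**4. Collinearity at full adherence.** Assume hours uniform on 20-24 in one arm (mean 22, variance 16/12 = 1.33) and 0 in the other.
- Between-arm variance of hours: 22²/4 = 121. Mean within-arm variance: 1.33/2 = 0.67.
- R² of hours with arm = 121/121.67 = 0.9945; correlation 0.997. Variance inflation = 1/(1 − 0.9945), about 182 (about 187 in the simulated samples).
- Hours vary only within the swaddling arm, so the slope has SE of about 1/√(40 × 0.24 × 1.33) = 0.28 per hour. The arm coefficient extrapolates that slope over 22 hours: 22 × 0.28 = 6.15.
- SE of arm is about √(0.62² + 6.15²) = 6.2, against 0.62 without hours. Simulation gave 6.53.
- Even the full design effect would then give z = 1.79/6.2 = 0.29. This result does not depend on how the harm arises.

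**5. Simulation under imperfect adherence.** The protocol expects some non-adherence but gives no rate, so rates, hours and dose-response are assumptions. There were 2,000 trials per scenario, 40 per arm, with log-odds of a non-Type 1 hip linear in hours.

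*Set A:* swaddling arm uniform 18-24 hours; non-adherence of 0-20% in the non-swaddling arm only, at 2-20 hours; risk 10% at 0 hours and 40% at 21.
- Power for arm: 0.81-0.88 without hours, 0.02-0.04 with hours.
- Median log odds ratio: 1.5-1.9 falls to 0.03-0.18.
- SE: 0.62 to 4.2 at full adherence; 0.58 to 1.48 at 20% non-adherence.

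*Set B:* swaddling arm uniform 20-24 hours; equal non-adherence in both arms; risk 10% at 0 hours and 40% at 22.

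| Non-adherence | Correlation of hours with arm | Median OR, without → with hours | Power, without → with hours |
|---|---|---|---|
| 0% | 0.997 | 6.64 → 1.15 | 0.89 → 0.04 |
| 10% | 0.91 | 4.68 → 0.91 | 0.78 → 0.03 |
| 30% | 0.73 | 3.05 → 1.04 | 0.51 → 0.05 |

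The power without hours also falls as adherence worsens. That loss is real dilution and has nothing to do with the covariate.

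**The case against.** The case against is substantial.

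- **Section 3.5 is the fuller rule.** Its between-arm criterion admits only differences at enrolment, and diary-based exposure cannot differ then. This stands for that criterion. The rate-ratio criterion has no such limit, and neither does the Table 3 footnote.
- **Table 2 leaves the exposure out.** It repeats the other seven rows of Table 1 and drops exactly these two. The baseline list in Section 3.5 omits them as well. This suggests that the authors did not see them as candidate covariates, but nothing in the protocol bars them.
- **The fall of the odds ratio to about 1 is built in.** The simulations let risk depend only on hours, so once hours are in the model the true arm coefficient is zero. This stands: the pull to the null is conditional on that mechanism, although the trial's own hypothesis makes it plausible. The collinearity in step 4 does not rest on it.
- **A null adjusted result would not stand alone.** Table 2 also reports the unadjusted odds ratio, and a standard error of 4 to 6 would be hard to overlook.

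A reader might infer that the plan definitely puts the exposure into the model and cancels the effect, so that a harmful practice would be reported as harmless. The documents do not support that. They contain two conflicting instructions, and only the literal annex leads there.

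A reader might also infer from the baseline list in Section 3.5, which ends with "Graf hip type, alpha angles at baseline and management", that the model would adjust for orthosis treatment and so condition on the outcome. That does not follow either. All enrolled newborns have Type 2a hips, for which Section 1 gives one routine pathway at birth, so management at baseline is essentially constant. It appears in none of the three tables.

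**Conclusion.** The point holds as a conflict within the protocol. Annex 4 misclassifies two post-randomisation exposure variables as baseline, and its footnote then admits them to the primary adjusted analysis. Section 3.5 and Table 2 point away from this but do not exclude it. If the annex is followed literally, the adjusted arm odds ratio is unusable for the primary question. At near-full adherence its standard error rises roughly seven- to tenfold (0.62 to 4.2 or 6.53, depending on the assumed spread of hours). With more non-adherence, it moves to about 1 if harm acts through hours, and power is at or below the 5% level. The exact sizes rest on the assumed adherence, hours and dose-response. That hours would be selected does not, short of a near-complete failure of the intervention. The defect touches the adjusted estimate of the primary outcome and should be corrected before analysis.

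**What to change.** 1. In Annex 4, move the rows for swaddling days and swaddling hours per day from Table 1 to a separate table of post-randomisation adherence.
2. Use these variables only in the per-protocol and correlation analyses.
3. In Section 3.5, for both covariate criteria, and in the Table 3 footnote, state that only variables fixed before randomisation may enter the intention-to-treat outcome models. This sentence would also exclude any management decided after randomisation, so that item needs no separate argument.

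The cost is an edit to one table shell and one sentence in two places. No data collection, sample size or timeline changes.
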